9.2 Haemoglobin Concentration and Absolute Reticulocyte Count

Haemoglobin concentration and absolute reticulocyte count will be summarised by dose group and overall by visit (Screening and Day 10) for the FAS/ITT Population. An additional summary table will present the change from baseline values at Day 10 and will include the baseline, Day 10 and change from baseline values for subjects with both baseline and Day 10 values. Baseline is defined as the last value observed before the first dose.

A listing of haemoglobin concentration and absolute reticulocyte count will be provided for the FAS/ITT Population.

10 SAFETY ANALYSIS

10.1 Adverse Events

All adverse events reported during the study will be listed for the Safety Population; the listing will contain an indicator for whether the event was considered as treatment emergent. An additional listing will be provided for all serious adverse events.

A summary overview of all adverse events by dose group and overall will be provided, which will present the number and percentage of subjects from the Safety Population satisfying each of the following categories:

- Any adverse event (AE);
- Any treatment emergent adverse event (TEAE);
- Maximum severity of TEAEs – mild, moderate, severe;
- Relationship of TEAE to study drug – not related, related;
- Action taken with study drug in relation to TEAE – dose not changed, dose reduced/increased, drug interrupted, drug withdrawn;
- Any TEAE leading to study discontinuation;
- Any serious adverse event (SAE);
- Maximum severity of SAE – mild, moderate, severe;
- Relationship of SAE to study drug – not related, related;
- Action taken with study drug in relation to SAE – dose not changed, dose reduced/increased, drug interrupted, drug withdrawn;
- Any SAE leading to study discontinuation;
- Any SAEs leading to death.

For the treatment emergent adverse events, the number, severity, relationship to study drug and action taken will be described by incidence tables. Subjects with multiple episodes of the same TEAE (i.e. same Preferred Term) will be counted once in these tables. Similarly, subjects with multiple severities for the same TEAE will be categorized by the maximum severity experienced; subjects with instances of the same TEAE recorded as both related and unrelated to study drug will be categorized as related and subjects with multiple actions taken within the same TEAE will be categorized according to the worst case. Actions taken include drug withdrawn, drug interrupted, dose reduced/increase and dose not changed (listed from worst case to best case).

Similar incidence tables will be presented for the serious adverse events. Separate incidence tables will also be presented for those TEAEs leading to withdrawal of study drug and to study discontinuation.

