In this paediatric PK study, children aged 10 to 17 years will be administered up to the adult dose of 30 mg BID. Given physiological control of intestinal absorption of iron uptake through the hepcidin pathway, and considering a total daily dose of 60 mg iron is within the approved dosage regimen for oral ferrous products in older children, iron overload in a 10-day exposure is considered not to be a risk. Furthermore, the metabolism of maltol through glucuronidation in the liver will be similar to adults. There is unlikely to be any great individual clinical benefit over 10 days of Ferric Maltol therapy, although the information gathered will be very important in establishing the dose(s) to be studied in the subsequent Phase 3 paediatric efficacy and safety study in IDA subjects. The risk to the subject related to study procedures has been assessed as very low. The study population will recruit subjects with iron deficiency or low-normal iron and who are otherwise generally well. The study population will include both female and male children and adolescents aged 10-17 age range. Pregnancy testing will ensure that pregnant female subjects do not enter the study, and that any subjects who become pregnant during the study are detected. The main study procedure risk is related to IV cannulation and blood sampling, with fainting, minor bleeding and bruising regarded as the main risks. Overall the benefit-risk of this study is considered positive.

Refer to the Investigator's Brochure for further details on risk/benefit assessment.

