6.4 SECONDARY ENDPOINTS

1. Descriptive analysis of transferrin, TIBC, UIBC and ferritin concentrations from PK samples collected on Day 1 and Day 10.
2. Descriptive analysis of non-transferrin bound iron (NTBI) concentrations from PK samples collected on Day 1 and Day 10.
3. Descriptive analysis of haemoglobin concentration and absolute reticulocyte count from haematology samples collected at Screening and Day 10.
4. Treatment-emergent Adverse Events (AEs) will be summarised.
5. Treatment-emergent Serious Adverse Events (SAEs) will be summarised.
6. Treatment-emergent Adverse Events leading to premature discontinuation of study drug/PK assessments will be summarised.
7. Clinical laboratory safety blood results at Screening and Day 10 will be summarised.
8. Changes in vital signs and 12-lead ECG will be summarised.
9. Concomitant medications will be summarised.

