3.3 Safety Endpoints

The safety endpoints for the study are:

1. Adverse Events (AEs) - Treatment Emergent Adverse Events (TEAEs), Treatment Emergent Serious Adverse Events (SAEs) and TEAEs leading to premature discontinuation of study drug/PK assessments;
2. Clinical laboratory safety blood results at Screening and Day 10;
3. Changes in vital signs and 12-lead ECG; and
4. Concomitant medications.

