4.4 Safety Measurements and Variables

4.4.1 Adverse Events

An adverse event (AE) is any untoward medical occurrence in a subject administered a pharmaceutical product and does not necessarily have a causal relationship with this treatment.

Any serious adverse event (SAE) that occurred from informed consent being obtained at the Screening Visit until two week after the last dose was to be recorded in the eCRF. Any AE that occurred from the time of dosing until the end of the study was to be recorded in the eCRF. The following details were to be recorded for each adverse event:

- Adverse event reported term;
- Start date and time and stop date;
- Outcome (fatal, ongoing/not resolved, recovered, recovered with sequelae, unknown);
- Severity (mild, moderate, severe);
- Relationship to study drug (related, not related);
- Action taken with study drug (dose increased, dose not changed, dose reduced, drug interrupted, drug withdrawn, not applicable, other, unknown);
- Other action taken, not related to study drug (none, concomitant medication required, non-drug therapy required);
- Cause study discontinuation (yes, no);
- Serious (yes, no); and
- If serious:
 - Death (yes, no);
 - Life-threatening (yes, no);
 - Inpatient hospitalisation (yes, no);
 - Prolongation of hospitalisation (yes, no);
 - Congenital anomaly or birth defect (yes, no);
 - Persistent or significant disability/incapacity (yes, no); and
 - Judged as medically significant (yes, no).

Adverse events will be coded using MedDRA version 19.0.

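### SAP 10.1 has no output for adverse events that end PK sampling, so a pre-specified safety endpoint can be undercounted

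*SAP*

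**What the plan says.** Protocol 6.4, item 6, reads "Treatment-emergent Adverse Events leading to premature discontinuation of study drug/PK assessments will be summarised". Protocol 12.2.2 repeats the item. SAP 3.3 carries the same definition into its safety endpoints: "TEAEs leading to premature discontinuation of study drug/PK assessments".

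The planned outputs are narrower. In SAP 10.1 the overview table has a row for "Any TEAE leading to study discontinuation" and rows for action taken with study drug. For the detailed tables the section says: "Separate incidence tables will also be presented for those TEAEs leading to withdrawal of study drug and to study discontinuation". SAP 14 states that nothing departs from the protocol.

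The adverse event record in SAP 4.4.1 offers three fields that might capture the event: action taken with study drug, the field "Cause study discontinuation (yes, no", and "Other action taken, not related to study drug (none, concomitant medication required, non-drug therapy required". None refers to PK sampling.

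**The concern.** The endpoint has a part with no planned row, table, flag or derivation. That part is also foreseeable in this trial. Protocol 5.6 names cannulation and blood sampling as the main procedural risk, "with fainting, minor bleeding and bruising regarded as the main risks". Under Protocol 11.1.1, events that the investigator relates to study procedures are adverse events, and under SAP 4.4.1 anything starting after the first dose is treatment-emergent. A faint after a post-dose draw that ends the session therefore meets the endpoint as defined.

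If such a child keeps taking capsules, or has already taken the last one, the tables may show no event for this endpoint even though sessions were cut short. A reader of the study report would then see a lower count of sampling intolerance in children aged 10-17 than the protocol's definition implies, with nothing to show that the definition had been narrowed.

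**Working it through.** The plan gives no figure to reproduce here. The check sets the definition beside the fields and outputs, then counts the samples involved.

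**Side by side**

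| Place | Stopping drug | Leaving the study | Stopping PK sampling |
|---|---|---|---|
| Protocol 6.4, 12.2.2; SAP 3.3 (definition) | yes | not named | yes |
| SAP 4.4.1 (AE fields) | yes | yes | no |
| SAP 10.1 (overview and incidence tables) | yes | yes | no |
| SAP 7.1 (disposition) | not separately | yes, with reason | no |
| SAP 7.2 (deviations) | no | no | missed sample, by visit, schedule group and timepoint; no reason or AE link specified |

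**Tracing one event.** Take a child who faints after the first post-dose draw on Day 10 and gives no further sample.

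1. The faint is a TEAE, so it enters the AE listing, the any-TEAE row and the incidence tables.
2. Action taken with study drug: SAP 10.1 says "Actions taken include drug withdrawn, drug interrupted, dose reduced/increase and dose not changed". SAP 4.4.7 has the last capsule taken that morning on site, so no drug is left to withdraw and the withdrawal table does not count the event.
3. Study discontinuation: the event reaches that table only if the site ticks yes. Neither document says whether stopping PK sampling qualifies.
4. The missed draw is a reportable deviation under SAP 7.2, with no planned link to the faint.

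The same path applies on Day 1 if the child carries on with the capsules: step 2 then fails because drug is continued, and step 3 again decides.

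**Samples involved.** Inputs: 36 subjects, 12 per dose group (Protocol 12.1, SAP 13); two post-dose samples on each of two PK days (Protocol 10.7.4, SAP 4.2.1).

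- Planned post-dose samples: 36 x 2 days x 2 = 144.
- Of these, after the final dose: 36 x 2 = 72, and 72/144 = 50%.
- One child as a share of a dose group: 1/12 = 8.3%.

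For half of the post-dose samples, then, the drug-withdrawal route is closed and the count depends entirely on the study-discontinuation field.

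**The case against.** The strongest reply is that the event is neither lost nor impossible to score. A reader might infer that after the Day 10 dose no route to the endpoint exists, because the child still attends Visit 4 and so has not left the study. The documents do not support that. Protocol 7.5 requires subjects who stop treatment early to return for the post-study visit, and note 4 to the schedule in Protocol 10.2 gives early discontinuers their final assessments at Visit 4. Attending Visit 4 is therefore compatible with study discontinuation. Protocol 7.5 also lists inability to comply with protocol requirements as a reason for discontinuation, and the yes/no field is still open on Day 10.

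A reader might also infer that such an event goes uncounted altogether. It does not: it is in the general TEAE tables and listings. AE start times and the timepoints of missed samples are recorded, so in 36 children the two listings can be matched by hand.

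Three further points stand. Refusing a needle is not in itself an adverse event, so refusal alone does not meet the endpoint. Protocol 5.6 rates the overall procedural risk as very low. The summary is descriptive, and no dose comparison or primary PK result depends on it.

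The reply does not supply the missing output. Counting the event through the study-discontinuation field relies on an unwritten convention that sites may apply differently.

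**Conclusion.** The gap is real and its consequence is limited. SAP 10.1 does not deliver one part of an endpoint that Protocol 6.4 and SAP 3.3 both define, and SAP 14 does not declare the narrowing. The count can be too low whenever a TEAE ends PK sampling, drug is not withdrawn, and the site leaves the study-discontinuation field at no.

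How often that would happen cannot be estimated: the documents give no rate of sessions cut short by adverse events and no rule for the field. Any probability of an undercount would rest on two unsupported assumptions, so none is offered. What can be said is that one misclassified child moves a dose-group percentage by 8.3 points. The conclusion assumes that the AE fields listed in SAP 4.4.1 are complete; an eCRF item for stopped sampling that the SAP does not mention would make the fix easier but would still need a table.

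**What to change.** In SAP 10.1, add to the overview and the incidence tables a category for any TEAE that led to early stopping of study drug or of PK assessments. Keep the existing drug-withdrawal and study-discontinuation outputs as its components.

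State the derivation. A TEAE qualifies if any of these holds:

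- action taken is drug withdrawn;
- the study-discontinuation field is yes;
- because of the TEAE, all remaining scheduled PK samples on that PK day, or those of the later PK day, were not collected.

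Settle the third condition by medical review of the missed-sample deviations against the AE records before database lock. A missed draw followed by a later collected one should not count, since sampling did not stop.

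The cost is a few lines of SAP text, one derived flag and the review of what should be few records. SAP 1 allows revision before database lock. The small downside is that SAP 7.2 specifies no reason for a missed sample, so the reason may have to come from comment fields or a site query. If the sponsor prefers the present tables, the narrowing of the endpoint should be declared in SAP 14.

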10.2 Safety Laboratory Parameters

The safety laboratory parameters (Haematology and Clinical Chemistry) will be summarised by dose group and overall by visit (Screening and Day 10) for the Safety Population. An additional summary table will present the change from baseline values at Day 10 and will include the baseline, Day 10 and change from baseline values for subjects with both baseline and Day 10 values. Shift tables (from Screening to Day 10) will also be presented the safety laboratory data. If the Screening retest is performed, the values of Screening retest will be used as baseline.

All safety laboratory data, including normal ranges and abnormal laboratory flags, will be provided in data listings for the Screened Population.

Pregnancy test results will be also be listed for the Screened Population.

10.3 Vital Signs

Vital signs data will be summarised by dose group and overall by visit (Screening, Days 1 and 10 and Follow-up) for the Safety Population. Change from baseline at each post-baseline visit (Day 10 and Follow-up) will be presented in a separate summary table and will include baseline, post-baseline values and change from baseline values for subjects with both baseline and specific post-baseline values. Baseline is defined as the last value observed before the first dose.

All vital signs data will be listed for the Screened Population and FAS/ITT Population.

10.4 12-Lead ECG Parameters

Continuous ECG parameters (Heart Rate, PR Interval, RR Interval, QRS Duration, QT Interval, QTcB Interval and QTcF Interval) will be summarised by dose group and overall by visit (Screening and Day 10) for the Safety Population. Change from baseline at Day 10 will be presented in a separate summary table and will include baseline, post-baseline values and change from baseline values for subjects with both baseline and Day 10 values. Baseline is defined as the last value observed before the first dose.

Overall interpretation will also be summarised by dose group and overall by visit. Shift tables (from baseline to Day 10) will also be generated for the overall interpretation results.

All ECG data will be listed for the Screened Population and FAS/ITT Population.

10.5 Physical Examination

Findings from the physical examinations will be listed for the Screened Population.

Shift tables (from Screening to Day 10) will be generated for the overall interpretation of the physical examination.

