10 STUDY PROCEDURES

10.1 DESIGN SCHEMATIC

10.2 SCHEDULE OF ASSESSMENTS

PERIOD	SCREENING	TREATMENT		POST-STUDY FOLLOW-UP
Visit Number	1	2	3	4
Visit Name	Screening Period ¹	PK Day 1	PK Day 2	Post-Study Safety Follow-up ⁴
Visit Day/Duration	Up to 14 days	Day 1	Day 10	3-10 days after treatment discontinuation
Informed Consent	X			
Demographics ⁷	X			
Medical History	X			
Concomitant Medications and Procedures	X	X	X	X
Physical Examination	X			X
Vital Signs ²	X	X	X	X
12-lead ECG ²	X		X	
Urine Pregnancy Test ³	X	X	X	X
Haematology, Clinical Chemistry and screening Iron markers blood sampling ³	X		X ⁶	
Eligibility Confirmation and Randomisation	X	X ³		
Dispense Study Drug		X		
Supervised morning dosing with Ferric Maltol		X	X	
Sparse PK Blood Sampling for Iron markers, maltol/maltol glucuronide and NTBI ^{5,6}		X	X	
Issue and Review of Subject Study Dosing Diary		X	X	
Subject to Return Study Drug for Accountability			X	
Adverse Events		X	X	X

1. A subject may be retested once for screening laboratory criteria that do not meet protocol in/exclusion criteria, so long as randomisation occurs no more than 14 days from the initial screening date (if eligible based on retest results).

2. Vital Signs – supine systolic/diastolic blood pressure, pulse rate and body temperature at each visit; 12-lead ECG at Screening and Day 10 (between 1h and 4h post-dose) - machine reported routine ECG parameters (heart rate, PR interval, RR interval, QRS duration, QT interval) and overall clinical ECG interpretation will be recorded in the eCRF.

3. Eligibility central laboratory sampling/assessments must be completed at Screening (Visit 1), before the subject is randomised and before the first dose of Ferric Maltol study treatment is taken. Screening parameters to be tested will be:

Haematology: red blood cell count, haemoglobin, haematocrit, mean cell volume (MCV), mean corpuscular haemoglobin (MCH), mean corpuscular haemoglobin (MCHC), white blood cell count (total and differential (% and absolute), absolute reticulocyte count and platelet count.

Clinical Chemistry: ALT, AST, alkaline phosphatase, gamma-glutamyl transpeptidase (GGT), total bilirubin, creatinine, amylase, blood urea nitrogen (BUN), phosphorous, sodium, potassium, chloride, calcium, total cholesterol, uric acid, glucose, total protein, albumin.

Iron Markers: serum iron, transferrin, transferrin saturation (TSAT), total and unsaturated iron binding capacity (TIBC, UIBC) and ferritin.

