Urine pregnancy test for female subjects of childbearing potential.

On Day 10 (Visit 3), haematology and clinical chemistry blood samples will be collected at one of the PK sampling times between 1h to 4h post dose). Female subjects of childbearing potential will undergo urine pregnancy tests pre-dose on Day 1 and Day 10 and at the Post-study visit.

4. Subjects who discontinue from the study prematurely should have final assessments conducted per Visit 4/Post-study Safety Follow Up, unless consent is withdrawn.

5. On PK study Days 1 and 10, all subjects will have baseline PK blood samples collected immediately prior to Ferric Maltol dosing (0h). Subjects will then have further PK blood samples collected at two (2) additional times between 0.5h and 6h after dosing on Days 1 and 10; the post-dose PK sample time collection windows will be 0.5-1h, 1.0-2.0h, 2.0-3.0h, 3.0-4.0h and 4.0-6.0h. Subjects will be assigned to the required post-dose PK blood sampling schedule in sequential order at the time of randomisation, based on current subject enrolment across all study sites. For each individual subject, the post-dose PK blood sampling schedule will be the same on Day 1 and Day 10. Post-dose blood samples should be collected within the time windows allocated only. N.B: For those subjects in PK Sample Schedule Group 1 (see summary table in Section 10.7.4), the PK blood samples for the 0.5-1h timepoint window should be taken at least 30 minutes before the PK blood samples for the 1-2h timepoint window on Day 1 and Day 10. Further details are provided in Section 10.7.2 and Section 10.7.4. After the required post-dose PK blood sampling is completed on Day 1 and Day 10, an individual subject can be discharged from the site, providing the Investigator has no ongoing safety concerns.

6. Iron markers to be tested from PK blood samples on Days 1 and 10 will be: serum iron, total and unsaturated iron binding capacity (TIBC, UIBC), transferrin, transferrin saturation (TSAT), ferritin and non-transferrin bound iron (NTBI).

7. A minimum of 25% of each gender and at least 3 subjects per age category (10 to 14y and 15-17yr) are to be enrolled in each Ferric Maltol dose group. Height (m) and body weight (Kg) will be measured at Screening (Visit 1) only.

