11.5 SAFETY ENDPOINTS

During the study, safety endpoints will be treatment-emergent AEs and SAEs, including clinically significant changes from baseline in vital signs, physical examination, routine clinical laboratory abnormalities (other than iron deficiency/anaemia indices) and ECG wave interval, waveform or rhythm.

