12.2.2 Secondary Endpoint Analyses

Secondary endpoints are:

1. Descriptive analysis of transferrin, TIBC, UIBC and ferritin concentrations from PK samples collected on Day 1 and Day 10.
2. Descriptive analysis of non-transferrin bound iron (NTBI) concentrations from PK samples collected on Day 1 and Day 10.
3. Descriptive analysis of haemoglobin concentration and absolute reticulocyte count from haematology samples collected at Screening and Day 10.
4. Treatment-emergent Adverse Events (AEs) will be summarised.
5. Treatment-emergent Serious Adverse Events (SAEs) will be summarised.
6. Treatment-emergent Adverse Events leading to premature discontinuation of study drug/PK assessments will be summarised.
7. Clinical laboratory safety blood results at Screening and Day 10 will be summarised.
8. Changes in vital signs and 12-lead ECG will be summarised.
9. Concomitant medications will be summarised.

In general, data for these secondary endpoints will be listed and summarised by dose group, as described in the SAP.

AEs will be categorised by primary system organ class and MedDRA preferred term as coded using the MedDRA dictionary. The number, intensity, relation to study medication and action taken will be described by incidence tables. SAEs will be discussed separately.

Vital signs, body weight and height will be evaluated and summarised with appropriate descriptive statistics.

Abnormal findings on physical examination and 12-lead ECG clinical interpretation will be described by shift tables with description of shift from baseline categories of normal to abnormal. 12-lead ECG parameters will be listed and summarised descriptively.

Screening clinical laboratory data will be listed and summarised with appropriate descriptive statistics and for Day 10 results, changes from Screening will be summarised.

Concomitant medications will be listed and summarised by WHO preferred term.

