2.2 Trial Design

This is a Phase 1, open label, randomised, repeat dose, parallel group study.

Approximately 36 eligible subjects aged 10-17 years were to be randomised at a ratio of 1:1:1 to one of three doses of Ferric Maltol (7.8 mg, 16.6 mg or 30 mg BID) for nine days (Days 1 to 9); a final single dose was then be administered on the morning of Day 10. Randomisation was to be stratified by age (10-14 years, 15-17 years) and gender (male, female) to ensure a minimum of 25% of each gender and at least three children per age group are enrolled in each Ferric Maltol dose group.

The planned study consisted for three study periods:

1. Screening Period;
2. Open-Label Treatment Period; and
3. Follow-Up Period.

Table 1 contains details of the study periods, study visits and timing of the visits. A short visit name has been generated to be included in tables and listings with limited space.

Table 1 Study Visits

Study Visit	Period	Study Day	Visit Name	
			Long	Short
1	Screening	-14 to -1	Screening	Screening
2	Open-Label Treatment	1	PK Day 1	Day 1
3	Open-Label Treatment	10	PK Day 10	Day 10
4	Follow-up	3 -10	Post-Study Safety Follow-up	Follow-up

The Screening Period consisted of one visit: Study Visit 1 (Screening) scheduled to take place within 14 days prior to the planned Open-Label Treatment Period for each subject. The purpose of this visit was to determine subject eligibility for the study.

The Treatment Period was to include two visits: Study Visit 2 (Day 1; PK Day 1) and Study Visit 3 (Day 10; PK Day 10).

The Follow-up Period included the last study visit: Study Visit 4 (Post-Study Safety Follow-up). This visit was to occur 3-10 days following completion of the Open-Label Treatment Period or premature discontinuation of study drug.

The schedule of procedures can be found in Table 2.

Table 2 Schedule of Procedures

Period	Screening	Open-Label Treatment	Follow-up	
Study Visit	1	2	3	4
Short Name	Screening	Day 1	Day 10	Follow-up ⁴
Day		1	10	
Informed Consent	X			
Demographics ⁷	X			
Medical History	X			
Concomitant Medications and Procedures	X	X	X	X
Physical Examination	X			X
Vital Signs ¹	X	X	X	X
12-lead ECG ²	X		X	
Urine Pregnancy Test ³	X	X	X	X
Haematology, Clinical Chemistry and screening Iron markers blood sampling ³	X		X ⁶	
Eligibility confirmation and Randomisation	X	X ³		
Dispense Study Drug		X		
Supervised morning dosing with Ferric Maltol		X	X	
Sparse PK Blood Sampling for Iron markers, maltol/maltol glucuronide and NTBI ^{5, 6}		X	X	

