4.4.5 Physical Examination

A brief physical examination was to be conducted at the Screening and Follow-up Visits. The examination was to include an assessment of general appearance, skin, head, eyes, ears, nose and throat, cardiovascular, respiratory, abdominal, gastrointestinal and musculoskeletal systems.

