6 GENERAL CONSIDERATIONS FOR DATA ANALYSIS

Statistical analyses will be performed using SAS® (Version 9.3 or later). All available data will be presented in subject data listings, which will be sorted by dose group, subject identifier and where appropriate, visit number and visit/assessment date.

Listings will contain data for all attended visits whether scheduled or unscheduled and visits will be listed in the order in which they were attended. Tables will only summarise data for the scheduled visits.

Dose groups will be displayed in all output using the following labels:

- Ferric Maltol 7.8 mg bid
- Ferric Maltol 16.6 mg bid
- Ferric Maltol 30 mg bid

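### The SAP's physical examination shift table ends at Day 10, a visit with no scheduled examination, so the table would be empty as written

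*SAP*

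**What the plan says.** SAP section 10.5 gives the rule for the table: "Shift tables (from Screening to Day 10) will be generated for the overall interpretation of the physical examination". The same section also provides a listing of examination findings for the Screened Population.

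The timing of the examination is set elsewhere, and consistently:

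- SAP section 4.4.5: "A brief physical examination was to be conducted at the Screening and Follow-up Visits".
- Protocol section 10.2, schedule of assessments: the row reads "Physical Examination X X", with the two marks under Visit 1 (Screening) and Visit 4 (post-study follow-up). The Day 1 and Day 10 cells are blank.
- SAP section 2.2, Table 2: the same two marks in the same columns.

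On the Follow-up visit, SAP section 2.2 says: "This visit was to occur 3-10 days following completion of the Open-Label Treatment Period or premature discontinuation of study drug".

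Protocol section 12.2.2 is the source of the commitment: "Abnormal findings on physical examination and 12-lead ECG clinical interpretation will be described by shift tables". It describes shifts from a normal baseline to abnormal and names no post-baseline visit. The Day 10 endpoint therefore first appears in the SAP.

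**The concern.** A shift table needs a baseline value and a later value for the same subject. Section 10.5 takes the later value from a visit at which the examination is not done, and passes over the one visit after the start of dosing at which it is. Applied literally, the rule gives a table with no shifts in it.

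At stake is an output that the protocol promises. Protocol section 11.5 also counts "clinically significant changes from baseline in vital signs, physical examination" among the changes covered by the safety endpoints. SAP section 14 declares no changes from the protocol, so the omission is not a declared departure. If a programmer noticed the problem and used Follow-up without a change to the text, the reported table would depart from the SAP with no record of why.

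**Working it through.** No power or error-rate figure is involved, and the plan states no number that could be reproduced. The check sets the scheduled visits against the visits each shift table uses.

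| Assessment | Scheduled at | Shift table in SAP | Do the visits match? |
|---|---|---|---|
| Haematology, chemistry | Screening, Day 10 | Screening to Day 10 (10.2) | Yes |
| 12-lead ECG interpretation | Screening, Day 10 | Baseline (Screening) to Day 10 (10.4) | Yes |
| Physical examination | Screening, Follow-up | Screening to Day 10 (10.5) | No |

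**Could another rule supply a Day 10 value?**

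1. *Unscheduled examinations.* SAP section 6 says: "Tables will only summarise data for the scheduled visits". An examination done ad hoc on Day 10 would appear in a listing but not in the table.
2. *Early discontinuers.* Protocol section 10.2, footnote 4: "Subjects who discontinue from the study prematurely should have final assessments conducted per Visit 4/Post-study Safety Follow Up". Their final examination is therefore a Visit 4 record, not a Day 10 record.
3. *Day 10 and Follow-up as one visit.* They are distinct. Follow-up falls 3-10 days after treatment ends, and SAP section 10.3 treats Day 10 and Follow-up as two separate post-baseline visits for vital signs.
4. *A misread table row.* SAP section 4.4.5 gives the examination visits in running text, so the conclusion does not depend on how the schedule tables were extracted.

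**Count of usable pairs**, with 36 planned subjects in 3 groups of 12:

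- Screening with Day 10, as written: 12 × 0 = 0 pairs in 3 groups, so 0 of 36.
- Screening with Follow-up: 3 × 12 = 36 pairs at most, before missed visits or withdrawn consent.

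Day 10 is the right endpoint for the laboratory and ECG tables. The wording in section 10.5 was probably carried over from those sections, but that is an inference.

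**The case against.** The contradiction itself is hard to dispute. The case on the other side is about consequence.

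- **Important findings still reach the safety tables.** Protocol section 11.1.1 requires examination findings that are clinically significant, and new or worse since baseline, to be reported as adverse events. Events are collected from first dose to study completion, which includes the Follow-up visit, and SAP section 10.1 tabulates treatment-emergent events by dose group, severity and relationship. This stands. What is lost is one cross-tabulation, chiefly of changes not judged clinically significant.
- **Physical examination is not an endpoint in its own right.** Protocol section 11.5 brings it in through adverse events, and neither the protocol's secondary endpoints (6.4) nor the SAP's safety endpoints (3.3) list it separately. This also stands: the error does not leave a named endpoint unanalysed.
- **No data are lost.** The Follow-up examination is still performed and listed. True, and the 0 of 36 should be read as the content of this table, not as missing data.
- **A programmer would probably notice.** Likely, but that does not make the text right, and a silent repair would be undocumented.
- **Changing the visit may not be enough.** Section 10.5 tabulates an overall interpretation of the examination, yet SAP section 4.4.5 and protocol section 10.4 describe a review by body system and define no overall categories, whereas the ECG interpretation has defined categories in SAP section 4.4.4. This is a fair but separate gap, best closed in the same edit.

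These points keep the matter minor. None of them makes the rule in section 10.5 workable.

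**Conclusion.** The concern holds. SAP section 10.5 contradicts SAP sections 2.2 and 4.4.5 and the protocol's schedule of assessments. As written it yields 0 of 36 scheduled pairs, where Screening to Follow-up would yield up to 36. It is an internal inconsistency rather than a debatable choice of method.

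The impact is one descriptive safety table that the protocol commits to and the SAP would not deliver. Adverse event tables, the subject listing and the primary pharmacokinetic analysis are unaffected. The count assumes the planned enrolment of 36 and the visit schedule as printed. The upper figure also assumes that every subject is examined at both Screening and Follow-up. The correction is desirable but would not change any main conclusion of the trial.

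**What to change.** In SAP section 10.5, replace Day 10 with Follow-up, so that the shift table runs from Screening to Follow-up, in line with section 4.4.5, Table 2 and the protocol schedule.

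Two small additions in the same edit would make the table fully specified: state the categories of the overall interpretation, or say how they are derived from the body-system findings, and name the Safety Population, which SAP section 5.1.3 already assigns to all safety summaries.

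The cost is a one-word correction plus, if adopted, a sentence or two. No procedure, visit or data collection changes. SAP section 1 allows revisions before database lock with the reasons given in the clinical study report. The documents do not say whether lock has occurred; if it has, the correction should be recorded in that report as a departure from the SAP text.
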